Our team is well-suited to conduct the trial. We bring together key members of the initial PTSD treatment model development team ([name] & [name]) with the investigator who took the lead on its adaptation for use in an addiction setting ([name]). Additionally, we have brought in leaders in VA on both the impact of PTSD on SUD treatment outcomes ([name]) and the effectiveness of SS in a VA addiction setting ([name]).

IV. RESEARCH DESIGN AND METHODS

A. Design

1. Overview

The proposed research will evaluate the effectiveness of the addition of a relatively simple, manual-guided CBT for PTSD to TAU in patients with co-occurring PTSD and SUD. One-hundred-sixty outpatients with comborbid PTSD/SUD will be randomly assigned to receive either CBT for PTSD in conjunction with standard TAU (n = 80) or TAU (n = 80) without additional individual treatment. Recruitment will target participants at three VA intensive outpatient addiction programs as well as participants with SUD and PTSD in those facilities who are not in the IOP. Participants will be assessed at baseline, post-treatment (approximately 4 months from baseline) and 6 month follow-up (approximately 10 months from baseline). Consistent with the goals of CBT for PTSD, the range of assessed outcomes includes both PTSD and substance use. Clinician adherence to the manual will be evaluated. Primary analyses will focus on the hypothesis that CBT for PTSD is more effective in reducing symptoms of PTSD than TAU.

2. Design considerations

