We proposed an additive design because we think it optimizes the internal and ecological validity of the study. We are interested in determining whether care as usual can be improved by adding CBT for PTSD. Specifically, we want to test whether it is desirable to add a new therapeutic regimen to TAU for substance abusing patients with the additional problem of PTSD. Thus, all participants must receive usual care for substance abuse treatment in addition to the new treatment. One concern that is sometimes raised with additive designs is that they do not control for the amount of treatment. To control for this, an alternative treatment can be offered to equate time. However, we do not think amount of treatment would be a plausible explanation for the expected difference between the CBT and TAU arms because the amount of CBT we propose to add is small relative to the amount of time in TAU treatment. Depending on the site, Veterans will receive between 87 and 225 hours of care in their intensive outpatient program, not including any mental health treatment Veterans may receive outside of the program. On average, CBT would only add 4-11% more treatment, depending on the program. We will carefully measure treatment services of the participants with SUD and PTSD who are not enrolled in one of the two intensive outpatient programs.

Another reason to consider comparing an active treatment to an alternative one is if the question focuses on whether the new treatment improves outcomes obtained by another standard of care. Currently there is no standard of care to use as a comparison. Although Seeking Safety appears to be the most widely used treatment in VA for patients with comorbid PTSD and SUD, the empirical evidence suggests it is no more effective in improving PTSD than control conditions such as relapse prevention and women's health education. Therefore, treatment as usual can serve as the control for whether observed outcome is due to any addiction treatment versus the addition of CBT specifically.

B. Sample and Recruitment

1. Inclusion criteria

Eligible subjects will meet the following inclusion criteria: (1) At least 18 years old, (2) Diagnosis of current substance use disorder, (3) Diagnosis of PTSD confirmed by the Clinician Administered PTSD Scale with a

total symptom score of 45 or more, (4) English speaking, (5) Agree to be audio recorded, and (6) Willing and able to provide informed consent.

2. Exclusion criteria

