At least 1,000 unique Veterans were seen at each site over the last fiscal year. Thus we expect that each recruitment site will see at least 1,500 unique patients over the 18-month recruitment period. We used the VA performance measure on continuity of care to estimate the number of patients seen who have been actively engaged in the IOP for at least 3 days. This measure corresponds to the number of patients that have no SUD contact in the prior 90 days and then have at least 3 SUD visits within 30 days. Next we conservatively estimate that 30% of SUD patients will meet criteria for PTSD (see background). Finally, we included only those we believed will be interested. Randomized trials of brief interventions for SUD patients found that approximately 60% of patients eligible for study participation agreed to participate. Assuming similar rates of participation, we expect that at least 60% of eligible participants will be interested. However, our study will have adequate power even if only 33% of patients agree to participate (See Table 1, Section B6 below, and the Inclusion and Enrollment Table included under Human Subjects).

Table 1. Recruitment and Enrollment

Site	# of SUD patients with SUD visit in 2008	Expected # of SUD patients available over 18 months	# SUD patients "successfully retained" based on continuity of care performance measure	Estimated # of PTSD cases (30%)	If 60% patients interested	If 33% patients interested
Tampa, FL	1000	1500	801 (53.4%)	240	144	80
Syracuse, NY	1200	1800	869 (48.3%)	267	160	88

Below is a revised recruitment table, assuming we are approved to recruit within the next two months through the end of the proposed study. These numbers show potentially eligible participants assuming we open recruitment up beyond the IOP in the two facilities. Numbers of veterans with comorbid PTSD and SUD were provided by PERC for FY 2012. (Note: numbers would be higher if we receive a one year no-cost extension)

Site	Estimated # of PTSD cases with SUD (25%)	If 60% patients interested	If 33% patients interested
Tampa, FL	1274	764	420
Syracuse, NY	901	540	270

In August of 2013, we made the decision to add a third site, White River Junction VA. This decision was made to boost enrollment and because of the cost-effectiveness of this particular site.

6. Power analysis

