2. TAU

Addiction treatment programs vary widely in VA. Data from PERC⁵¹ provide a sense of typical IOP services. 95% of all SUD IOP programs report providing group and/or individual psychotherapy to their patients. Just over half of the programs (57%) report that their patients participate in on-site SUD-related self help groups, such as Alcoholics Anonymous. Only 11% of programs offered contingency contracting. The majority of programs conduct a psychiatric assessment of SUD patients (78%) and about half receive psychiatric treatment (54%) or medication (41%) for a co-morbid psychiatric disorder.

The Tampa Alcohol and Drug Abuse Treatment Program (ADATP) is a 3 week IOP that consists of a 7 day, 4 hours per day, program. Relapse prevention, aftercare groups, and family sessions are offered additionally in the afternoon and evenings. The philosophy of the ADATP is based on an understanding of alcohol and drug abuse/dependence as a complex biopsychosocial illness. The major thrust of the treatment approach is derived from the 12-step model of recovery with additional emphasis on educational and cognitive-behavioral approaches. Each patient's individual recovery program has its own structured aftercare component, which is an integral part of treatment. Patients are strongly encouraged to participate in voluntary substance recovery organizations such as Alcoholics Anonymous (AA), Al-Anon, Narcotics Anonymous (NA), Cocaine Anonymous, and Adult Children of Alcoholics (ACOA). The ADATP program includes a six week dual diagnoses treatment program for patients who have co-occurring substance abuse and mental health disorders. The focus is on evaluation, stabilization, and intensive treatment. This phase includes individual and group therapy, educational classes, therapeutic outings, and medication management.

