The Syracuse Substance Abuse Treatment Service offers a six week IOP that consists of a 3 day, 4 hours per day, group treatment program based on a cognitive-behavioral treatment philosophy. The first hour of the program is focused on meditation and one time per week, patients receive acupuncture. The second hour is education; topics include education about cognitive-behavioral strategies (e.g., relapse warning signs) and other relevant topics (e.g., dealing with medical problems). The final 2 hours are group psychotherapy that are tailored to the needs of the group based on a CBT approach. Each patient is also required to attend an hour of individual counseling every other week. Twelve step participation is recommended depending on patients' needs but not required. The program also offers a dual-diagnosis group for patient who are mentally ill and chemically addicted and an aftercare program that teaches relapse prevention.

The White River Junction Residential Recover Center (RRC) program is offered as a six week intensive residential program specifically providing tandem evidence based treatments for co-morbidities such as PTSD, Major Depressive Disorder, and accommodation for either cognitive effects of PTSD or of traumatic brain injury.

To determine actual level of involvement in the IOPs, we will extract from the electronic medical record (i.e., Vista) days and types of SUD treatment received as well as additional services including mental health and primary care visits. We will also extract utilization records for participants who are not in IOP programs. In addition, all participants will provide information on a treatment services interview.

D. Therapist selection, training, supervision and quality monitoring

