$$E(Y_{ij}) = \beta_1 + \beta_2 Time_{ij} + \beta_3 Time_{ij}^2 + \beta_3 Group_i + \beta_5 Time_{ij} XGroup_i + \beta_6 Time_{ij}^2 XGroup_i$$

Finally, we will contrast of the group population means across time points. For example, mean difference $\mu_1 - \mu_2$ is likely to be 0 at baseline if randomization is successful. With the different impact of treatments, mean difference might be 10 (on the CAPS scale) at end of study. We would like to test whether this change in mean difference is significant. This is our hypothesis 1 and 2.

2. The effects of CBT on retention

Hypothesis 3 (secondary): Patients who receive CBT will have better retention in the addiction treatment program relative to patients who receive TAU as measured by the proportion of expected days of treatment attended.

For patients in IOPs, we will calculate the proportion of substance abuse treatment completed as a percentage of the full treatment. Using this completion proportion as our dependent variable, we will conduct a multivariate linear regression analysis that includes variables such as treatment assignment, demographic information, and baseline symptom severity as potential covariates, for example:

$$E(Y_i) = \beta_1 + \beta_2 Group_i + \beta_3 CAPS_{i0} + \beta_3 AGE_{i0} + \beta_4 SEX_{i0}$$

Where i0 stands for the ith individual's measurement at baseline (time=0).If, for example, β_2 is not significantly different from 0, then the two groups do not differ in terms of completion proportion when adjusted for age, gender, and baseline symptom severity as measured by CAPS.

Data on utilization and retention will be extracted from medical records using CAPRI or JLV. The HIPPA Authorization and the Informed Consent both clearly state that this information will be obtained from their medical records.

3. Exploratory analyses

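### Hypothesis 3 (retention) has an outcome only for patients in intensive outpatient programmes; randomised patients outside them do not contribute, and the third site and the site covariate are left open

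*Combined protocol and SAP*

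**What the plan says.** Hypothesis 3 appears in section I (Specific Aims) and section IV.G.2 (The effects of CBT on retention) as a comparison of CBT with TAU patients. Neither statement restricts it to a type of programme. IV.G.2 then gives the calculation: "For patients in IOPs, we will calculate the proportion of substance abuse treatment completed as a percentage of the full treatment". That proportion is the dependent variable of a linear regression, illustrated with terms for group, baseline CAPS, age and sex.

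Recruitment is wider than the IOPs. Section IV.A.1 (Overview) targets "three VA intensive outpatient addiction programs as well as participants with SUD and PTSD in those facilities who are not in the IOP". Section IV.C.2 (TAU) adds: "We will also extract utilization records for participants who are not in IOP programs". Section IV.E.3 (Outcomes) likewise plans to extract the type and number of usual-care SUD visits.

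The programmes are counted differently from section to section. IV.A.1 has three IOPs. IV.A.2 (Design considerations) refers to patients "who are not enrolled in one of the two intensive outpatient programs". IV.C.2 says that the White River Junction "program is offered as a six week intensive residential program". IV.F (Procedure) stratifies randomisation by site and puts the number of sites at two, although IV.B.4 (Sites) names three.

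Section IV.G.1, in describing the longitudinal models, lists site as a possible covariate and keeps only covariates that significantly reduce error variance.

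**The concern.** A named secondary hypothesis is worded for the whole trial but answered in part of it. A reader of the final report could take the retention result as applying to all randomised patients when those outside the IOPs contribute nothing.

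The part itself is not pinned down. The plan does not say when a patient's programme status is determined, and that status is not a stratification factor. Whether the residential site counts as an IOP for this purpose could be decided after the data are seen.

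Separately, a factor used to stratify randomisation is missing from the example model. Elsewhere it is subject to a significance rule.

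**Working it through.** **1. Who is randomised and who receives a retention value.**

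| Patients | Randomised? | SUD use extracted? | Hypothesis 3 outcome defined? |
|---|---|---|---|
| IOP (Tampa, Syracuse) | Yes (IV.A.1, IV.F) | Yes (IV.C.2, IV.E.3) | Yes (IV.G.2) |
| White River Junction residential | Yes (IV.B.4) | Yes | Depends on whether it counts as an IOP |
| Not in a programme | Yes (IV.A.1; opening of IV.G) | Yes (IV.C.2) | No |

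Section IV.G asks for analysis by assigned group, but that does not create an outcome where none is defined. The chi-square test for retention mentioned in IV.G.1 has no stated population or cut-off, so it does not fill the gap.

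**2. The plan's own figure.** No sample size or power is stated for hypothesis 3. The 160 in Table 2 (IV.B.6) belongs to the CAPS analysis. At d = 0.40 it is reproduced by a time-averaged comparison with three measures and correlation 0.60:

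- Per arm: 2(1.96 + 0.84)² × (1 + 2 × 0.60)/3 ÷ 0.40² = 71.95, rounded up to 72.
- Total with 10% loss: 144/0.90 = 160, as stated.

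Retention is measured once per patient, so it gains nothing from repeated measures and Table 2 does not carry over.

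**3. Precision for hypothesis 3.** Half-width of the 95% interval in SD units = 1.96 × √(2/n per arm), assuming equal arms and no lost records. The IOP share is not in the documents, so 75% and 50% are assumptions.

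| IOP share | N (per arm) | Half-width | Power at d = 0.45 |
|---|---|---|---|
| 100% | 160 (80) | 1.96 × √(2/80) = 0.31 SD | 0.81 |
| 75% | 120 (60) | 1.96 × √(2/60) = 0.36 SD | 0.69 |
| 50% | 80 (40) | 1.96 × √(2/40) = 0.44 SD | 0.52 |

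**4. Omitting site.** If site explains a share R² of the outcome variance, adjusting multiplies the standard error of the treatment effect by about √(1 − R²). The R² values are assumptions.

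- R² = 0.05: 0.975, a fall of 2.5%
- R² = 0.10: 0.949, a fall of 5%
- R² = 0.20: 0.894, a fall of 11%

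Because allocation is stratified by site, leaving it out costs precision; it does not bias the comparison.

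**The case against.** The best defence is that the restriction is deliberate and openly stated. Retention is measured against expected days, and a patient outside a programme has no stated expected days. If programme status precedes randomisation, the IOP comparison is unbiased. IV.A.2 and the programme descriptions in IV.C.2 agree on two IOPs plus one residential programme, so IV.A.1 may simply be loose, and the two sites in IV.F are a stratification count rather than a definition of the hypothesis 3 population. The regression is only an example with an open covariate list, and a percentage of each programme's full treatment already scales for length.

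Much of this stands. It shows that the comparison can be valid. It does not supply the date at which status is fixed, a decision on White River Junction, a use for the non-IOP records, or a limit on the conclusion. Scaling for length also does not remove differences between sites in how well patients attend.

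A reader might infer three stronger points, which the documents do not support.

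- *The IOP subset is about 23% of the trial, or 37 patients.* This divides the 507 cases in Table 1 (240 + 267) by the 2,175 in the revised table (1,274 + 901), both in IV.B.5. The first count has passed a continuity-of-care filter intended "to estimate the number of patients seen who have been actively engaged in the IOP for at least 3 days". No such filter is described for the second: "These numbers show potentially eligible participants assuming we open recruitment up beyond the IOP in the two facilities". Without the filter, 0.30 × (1,500 + 1,800) = 990, and 990/2,175 is about 46%, or 73 patients and a half-width of 0.46 SD. The PTSD rates (30% and 25%) and source years also differ, and a pool share does not fix the enrolled share.
- *At Tampa retention is largely settled before most CBT sessions.* The Tampa programme "is a 3 week IOP that consists of a 7 day, 4 hours per day, program", but the same paragraph describes a six week track for patients with co-occurring mental disorders, which describes this trial's patients. Six weeks could hold 6 weekly or 12 twice-weekly sessions.
- *Days attended before randomisation shrink the effect by 14% or 17%.* These are 3/21 and 3/18. Denominators of 21 and 18 days at 4 hours give 84 and 72 hours, both below the 87-hour minimum in IV.A.2, so they are not established. The three days come from a recruitment estimate and are not an eligibility rule. A constant number of earlier days leaves the standardised effect unchanged.

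**Conclusion.** The concern holds as a problem of scope and definition for a secondary hypothesis. Hypothesis 3 is stated generally and answered only for IOP patients. Whether the third site belongs to that group is unclear, and site is not secured in the model.

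The documents do not show that the IOP-only comparison is biased. It is valid if programme status is fixed at randomisation, and its conclusion is then confined to that subset. The cost in precision depends on an unknown share: from 0.31 SD with everyone to 0.36 SD or 0.44 SD at assumed shares of 75% or 50%. Adding site gains about 2.5% to 11% in standard error if it explains 5% to 20% of the variance, also an assumption. None of this touches the primary CAPS analysis.

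**What to change.** 1. Classify each patient as IOP, residential or neither, using information available at randomisation. State before data are examined by arm whether White River Junction enters hypothesis 3. Reconcile IV.A.1, IV.A.2, IV.C.2 and IV.F on the number and type of programmes and sites, and report N by arm for the analysed group.
2. Put site in the hypothesis 3 regression as a fixed covariate, outside any significance rule.
3. Add a supportive analysis in all randomised patients of engagement in SUD treatment over one fixed window after randomisation, leaving out the study's own CBT visits.
4. Limit the conclusion from the IOP-based analysis to programme patients.

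As an optional clarification, count days from randomisation in the track in which the patient is then enrolled. This has little effect on the standardised result.

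The cost is mainly analysis-plan wording, because the utilization records are already to be extracted. Visit dates and a flag for study CBT visits must be kept. The drawback of item 3 is that it measures engagement in SUD care rather than completion of a programme, so it can support hypothesis 3 but not replace its outcome.
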